**1. Introduction and Purpose:**

**Background:** Insufficient growth before or after birth and insufficient nutrient intake in preterm infants in the neonatal intensive care unit (NICU) are associated with growth insufficiency and neurodevelopmental impairment at follow-up. Both extremely low gestational age (GA) neonates (ELGANs) and small for gestational age (SGA) (weight < 10th percentile for GA) neonates may develop signs suggestive of metabolic syndrome during the first 3 years of life. Low birth weight (BW), prematurity and rapid or disproportionate weight gain (with increased weight for length) during the first months after birth are associated with signs of metabolic syndrome in adults.

In preterm infants fed human milk, milk needs to be fortified to meet nutrient recommendations. Fortification can be 1) standard, 2) individualized (adjusted based on daily human milk nutrient analysis and milk volume), or 3) optimized (adjusted based on growth rate and serum analyses).

**The first specific aim** will determine whether individualized and optimized nutrition during hospitalization results in improved growth in the neonatal intensive care unit (NICU) in extremely low gestational age (GA) neonates (ELGANs, <29 weeks) and in small for GA (SGA, birth weight <10th percentile for GA) preterm infants compared with optimized nutrition.

**The second specific aim** will determine whether individualized and optimized nutrition in the NICU improves neurodevelopmental outcomes (acquisition of development milestones) and reduces the risk of disproportionate growth (i.e., excess fat) in the NICU and findings suggestive of metabolic syndrome in the first 3 years of life.

### **Hypotheses:**

- Primary hypothesis:** In preterm infants (GA <29 weeks or GA <35 weeks and SGA) individualized and optimized nutrition will increase velocity of growth (weight gain velocity by  $2 \text{ g} \times \text{kg}^{-1} \times \text{day}^{-1}$  and length velocity by 0.2 cm per week) from birth to 36 weeks of postmenstrual age (GA plus postnatal age) in comparison with optimized nutrition.
- Secondary hypotheses:** Individualized and optimized nutrition will improve neurodevelopmental outcome and reduce the risk of disproportionate growth (excess fat) in the NICU and findings suggestive of metabolic syndrome in the first 3 years of life.

#### Primary study endpoint (Aim 1):

- Growth velocity (rate of weight gain [ $\text{g} \times \text{kg}^{-1} \times \text{day}^{-1}$ ] and length velocity [ $\text{cm} \times \text{week}^{-1}$ ]) from birth to 36 weeks of PMA (or discharge if patient is discharged earlier than 36 weeks PMA) will be calculated using Patel's geometric method.

#### Secondary endpoints (Aim 2):

In the NICU:

- Disproportionate growth (abdominal circumference, subscapular skinfold and BMI greater than their respective 90th percentiles for age) at 36 weeks of PMA or discharge if patient is discharged earlier than 36 weeks PMA
- Body composition analysis using air displacement plethysmography (Pea Pod)
- Blood pressure (systolic and mean, calm or sleeping) at 36 weeks PMA and discharge
- Hypertension, defined as systolic blood pressure >99th percentile for PMA for at least 24 hours while sleeping or calm
- Blood sample for measurements of cholesterol, fats, cystatin C, adipokines and some blood markers that may indicate a higher risk for development of diabetes or metabolic syndrome at discharge or 36 weeks of PMA, whatever comes first;
- Bacterial diversity and ratio of Firmicutes to Bacteroidetes (F:B) in stool samples (1) at 28 days of age and (2) at 36 weeks or discharge if earlier than 36 weeks
- Body composition analysis using air displacement plethysmography (Pea Pod) at 36 weeks of PMA or discharge if patient is discharged earlier than 36 weeks PMA

At the Follow-up Clinic (Thrive Clinic, [name]), a state-of-the-art facility with >95% follow-up rate, at 6, 12, & 36 months chronological age & 18-26 months adjusted age (PNA corrected for prematurity):

- Neurodevelopment (Bayley III) scores (cognitive and language composite) at 18-26 months adjusted age
- Findings suggestive of metabolic syndrome: disproportionate growth (excessive fat mass) and high systolic blood pressure at each visit at 6 months, 1, 2 and 3 years of age
- Serum levels of cholesterol, fats, cystatin C, adipokines and some blood markers that may indicate a higher risk for development of diabetes or metabolic syndrome at 1 and 3 years of age
- Body composition analysis using air displacement plethysmography (Pea Pod) at 6 months of age
- Body composition analysis using Dexascan (Hologic Horizon A) at 1 and 3 years of age □ Relationship between stool bacterial diversity and F:B ratio, growth and obesity Stopping Rules:

- Less than 10 patients recruited in 12 months
- Mortality in enrolled patients significantly higher than in non-enrolled patients ( $P<0.01$ )
- More frequent necrotizing enterocolitis in enrolled patients ( $P<0.01$ )

Purpose: To provide preliminary data for a multicenter randomized trial to test whether individualized and optimized nutrition in ELGANS and SGA preterm neonates improves neurodevelopmental outcomes and reduces the risk of metabolic syndrome. This could be of major public health significance.

Standard of care: Feeding human milk rather than formula has several advantages for preterm infants including decreasing the frequency of necrotizing enterocolitis and infections. However, human milk does not provide enough calories or proteins, leading to less growth; therefore, human milk must be supplemented with human milk fortifier, and for some babies, additional protein or fat. The amount of protein and fat in mother's breast milk and donor milk is highly variable, often leading to insufficient growth velocity. There are three ways to fortifying human milk for preterm infants: (1) Standard, fixed dosage fortification; (2) Adjustable (optimized) fortification using growth velocity to modify caloric supplementation and a surrogate for protein sufficiency to modify the dosage of protein fortification, and (3) Targeted (customized, individualized) fortification or fortification triggered by poor growth and results from human milk analysis. One small randomized trial showed that growth of preterm infants in the NICU improved using adjustable supplementation of human milk based on weekly BUN levels. Other authors have used this approach and observed better growth without any toxicity. At Parkland we have used this approach for more than a decade: adjustment of human milk fortification is based on growth velocity and weekly serum BUN and albumin levels; protein intake is increased weekly until BUN is greater than 10 mg/dl and albumin is  $> 3$  g/dl.

Targeted individualized supplementation of human milk with fat has been done based on creamatocrit (measurement of fat layer after centrifugation); this method was shown inferior to near infrared spectrophotometry, which has become the gold standard for human, dairy or animal milk analysis. Hair showed in a small RCT that targeted supplementation of human milk with fat (human milk cream) based on serial measurements of human milk nutrients using near infrared spectrophotometry, increased weight gain and linear growth in preterm infants with birth weight 750-1250 grams. Several centers have used targeted individualized nutrient supplementation successfully. Individualized supplementation was associated with improved growth and less gastroesophageal reflux compared to routine supplementation based on assumed nutrient contents. Analysis of donor milk nutrient is standard of care in donor milk banks in the US.

Rationale for the RCT: There are three ways to fortifying human milk for preterm infants: (1) Standard, fixed dosage fortification; (2) Adjustable (optimized) fortification using growth velocity to modify caloric supplementation and a surrogate for protein sufficiency to modify the dosage of protein fortification, and (3) Targeted (customized, individualized) fortification or fortification triggered by poor growth and results from human milk analysis. Methods 2 and 3 have been shown by multiple observational studies and each by one randomized controlled trial (RCT) to be superior to the first method, but methods 2 and 3 have never been compared in an RCT.

We plan a RCT to compare standard of care at Parkland (optimized supplementation) with individualized supplementation in high-risk infants. This RCT will determine whether growth of preterm at high risk for growth insufficiency can be improved by targeted daily supplementation based on (1) serial milk analyses in addition to standard of care and (2) the amount of enteral feeding given daily. Patients randomized to the control arm will receive standard of care at Parkland, which involves adjustment of human milk fortification based on growth velocity and weekly serum BUN and albumin levels; protein intake will be increased weekly until BUN (adjusted for creatinine) is greater than 10 mg/dl and albumin is  $> 3$  g/dl. Patients in the treatment arm be part of a quality improvement including targeted daily supplementation of human milk based on serial milk analyses using near infrared spectrophotometry to meet expected requirements based on postmenstrual age and physiologic status; milk intake and fortification will be further adjusted based on growth velocity and weekly serum levels of BUN and albumin levels, which will be used as gold standard.

Status of the device: Measurement of nutrients in human milk has been used by several investigators and has been shown to improve growth compared with standard fortification. Standard for human milk bank is to analyze pooled human milk samples and to provide this information on each milk bottle to the neonatal intensive care unit (NICU). However, devices for analyzing human milk samples have not been approved by the FDA for analyzing individual mother's milk for making individual decisions in the neonatal intensive care unit (NICU). Three devices are currently available in the US for human milk analysis: The Calais Human Milk Analyzer, the SpectraStarTM 2500 XL Neonatal Analyzer (which has now replaced the previous 2400 version) and the Foss FT120. We plan to use the SpectraStarTM 2500 XL. This device has been validated in one study. It is the only device available in the US that was used in a randomized clinical trial, which showed improved growth (weight gain and linear growth) in the group in which nutrition was adjusted based on readings of human milk composition using this device. We believe this device is a non-significant risk device because

1. Measurement of nutrients in human milk has been used in several centers to adjust fortification of human milk for preterm infants, and has been shown in one randomized trial to improve growth without any risk to the infants.
2. Infants randomized to the treatment arm will have growth velocity and BUN and serum electrolytes measured regularly, as is done for standard of care, to make sure that adjustment of human milk fortification is not exceeding needs for each infant.
3. The Institutional Review Board of Baylor College of Medicine and Affiliated Hospitals and the University of Texas Health Science Center at San Antonio have approved a randomized trial that used this device and was conducted at Texas Childrens and San Antonio without an IDE (Hair et al, attached).

Status of relevant research:

Several studies have shown major variability in human milk nutrients. The best method for measuring nutrients in human milk is near infrared spectrophotometry. Supplementing human milk based on its measured composition has been standard of care in several NICUs for years. Measuring nutrients in human milk to provide individualized milk fortification was shown to improve growth (weight gain and linear growth) without side effects in a randomized trial at Texas Children's. However, no RCT has been conducted to compare individualized targeted supplementation with adjustable optimized supplementation.

The bowel utilizes a high amount of enterally derived threonine and glutamine, two essential amino acids, for its own metabolism and production of mucin; suggesting that growth might improve by discounting enteral contribution to protein intake while providing less than  $75 \text{ ml} \times \text{kg}^{-1} \times \text{day}^{-1}$  of enteral feeding; such an approach has been used routinely in the Netherlands but has not been tested in a RCT; no evidence has been published at this point to show whether this approach improves any of the clinical outcomes.

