#### Secondary endpoints (Aim 2):

In the NICU:

- Disproportionate growth (abdominal circumference, subscapular skinfold and BMI greater than their respective 90th percentiles for age) at discharge or 36 weeks of PMA (whatever comes first)
- Air displacement plethysmography at discharge: this will be done using the Pea Pod, a noninvasive instrument that is FDA approved for measuring fat in neonates and infants. This apparatus measures body volume; taking into account body weight and accepted assumptions, the analysis generates the percentage of fat and lean body mass. This is the gold standard method for body composition in neonates and young infants, for which normative data are available.
- Blood pressure (systolic and mean, calm or sleeping) at 36 weeks PMA and discharge
- Hypertension, defined as systolic blood pressure >99th percentile for PMA for at least 24 hours while sleeping or calm
- Serum levels of cholesterol, fats, cystatin C, adipokines and some blood markers that may indicate a higher risk for development of diabetes or metabolic syndrome at discharge or 36 weeks of PMA, whatever comes first; these blood samples will be obtained at the same time as other blood samples for clinical indication

At the Follow-up Clinic (Thrive Clinic, [name]), a state-of-the-art facility with >95% follow-up rate, at 6 months, 12 & 36 months chronological age & 18-26 months adjusted age (PNA corrected for prematurity):

- Body composition using Pea Pod at 6 months of age
- Neurodevelopment (Bayley III) scores (cognitive and language composite) at 18-26 months adjusted age
- Findings suggestive of metabolic syndrome: disproportionate growth (excessive fat mass) and high systolic blood pressure at each visit;
- Serum levels of cholesterol, fats, cystatin C, adipokines and some blood markers that may indicate a higher risk for development of diabetes or metabolic syndrome at 1 and 3 years of age (half a teaspoon of blood); these blood samples will be obtained at the same time as other blood samples for clinical indication

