- Stools will be collected and frozen for later analysis of microbiome diversity, Firmicutes:Bacteroidetes ratio and metagenomics. Samples will be collected every other week from randomization to discharge.
- Follow-up at 12 and 36 months chronological age and at 18-26 months adjusted age:
- Weight, length, FOC, abdominal circumference, skinfold thickness, two calm blood pressure measurements using Doppler amplification with the exact same protocol as previously described, history of steroids and antibiotics at each visit
- Neurodevelopment (Bayley III) cognitive and language composite scores at 18-26 months
- Serum levels of cystatin C, creatinine, cholesterol (total, LDL, HDL), triglycerides, Leptin, Adiponectin, Resistin, IL-6 and TNF alpha at 1 and at 3 years of age (half a teaspoon of blood)
- Whole-body Dexascan to analyze body composition including percentage of fat at 1 and 3 years of age

Procedures: Patients will be randomized to either (a) Optimized and individualized nutrition by adjusting milk fortification based on daily measurements of macronutrients in mother's own milk or information on milk from the milk bank or (b) optimized (standard of care at Parkland), i.e., assuming macronutrient concentration in human milk based on available literature and summing enteral and intravenous protein intake. Patients will be followed for growth parameters in the neonatal intensive care unit and for growth, neurodevelopment and signs suggestive of metabolic syndrome in the low birth weight clinic until 3 years of age.

Maximum number of consented patients: 200; this will allow attrition for comfort care, deaths before 36 weeks PMA and withdrawal from the study; we expect to recruit approximately 150 patients into the study with a goal of 100 patients reaching endpoint at 36 weeks PMA

Duration of the study: 6 years: recruitment for 2 years, follow-up for 3 years, analysis for 1 year

Reason for removing from the study: comfort care, withdrawal by the parents

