#### **14. Biostatistics:**

The primary outcome variable (growth) will be analyzed by intention to treat (i.e., as randomized). Continuous variables including the primary outcome will be analyzed using Student's t-test or analysis of variance and a generalized linear model (to determine the effect of the intervention while taking into account co-variates and confounding variables). Dichotomous variables will be analyzed using chi-square analysis and by estimating relative risk using robust Poisson regression in a generalized estimating equation model. Subgroup analyses will be done to compare the 3 strata (AGA 23-28 weeks, SGA 23-28 weeks and SGA 29-34 weeks) and to compare SGAs due to insufficient calories (e.g., preeclampsia, low placental insertion) vs. constitutionally small neonates (e.g., congenital infection, genetic anomaly, short parents). A probability value  $<0.05$  will be considered statistically significant. Secondary outcome variables will be analyzed according to appropriate statistical techniques.

Sample size analysis: Based on the number of patients delivered at Parkland during the last 10 years, we expect that 342 (1140x3/10) eligible neonates will be delivered over 3 years. We anticipate enrolling half in the study and expect that 2/3 will survive to 36 weeks PMA. Thus we will enroll 150 patients to yield a 100 patients available for the primary outcome and to have 80% power using 2-tailed Student t-test (alpha error 0.025) to detect an increase in weight gain velocity in the NICU by  $2 \text{ g} \times \text{kg}^{-1} \times \text{day}^{-1}$  (standard deviation  $3 \text{ g} \times \text{kg}^{-1} \times \text{day}^{-1}$ ) and 95% power (alpha error 0.001) to detect an increase in length velocity by 0.2 cm per week (standard deviation 0.2 cm per week), taking into account clustering due to twins and multiples. We will have  $>80\%$  power for both outcomes (alpha error 0.05).

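### Follow-up systolic pressure is listed as an endpoint only in the form of a high/not-high cut with no stated threshold; listing the measured value as well would recover power at almost no cost

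*Combined protocol and SAP*

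**What the plan says.** **Follow-up endpoint.** The secondary endpoints in Section 1 include, among findings suggestive of metabolic syndrome, "high systolic blood pressure at each visit at 6 months, 1, 2 and 3 years of age". Section 3 repeats this as "disproportionate growth (excessive fat mass) and high systolic blood pressure at each visit". Neither place gives a cut-off, percentile or reference population for high.

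**NICU endpoint.** The NICU part of the same list has two separate blood-pressure endpoints. One is the value: "Blood pressure (systolic and mean, calm or sleeping) at 36 weeks PMA and discharge". The other is a yes/no endpoint with a stated threshold: "Hypertension, defined as systolic blood pressure >99th percentile for PMA for at least 24 hours while sleeping or calm".

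**Measurement.** Under Other measurements in Section 3, the follow-up schedule includes "two calm blood pressure measurements using Doppler amplification with the exact same protocol as previously described". The visits for that schedule are given as "Follow-up at 12 and 36 months chronological age and at 18-26 months adjusted age". Six months is not among them.

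**Analysis.** Section 14 states: "Dichotomous variables will be analyzed using chi-square analysis and by estimating relative risk using robust Poisson regression in a generalized estimating equation model". Continuous variables, not only the primary outcome, go to a t-test or analysis of variance and a generalized linear model. A closing sentence leaves secondary outcomes to whatever technique is appropriate. No sentence assigns a method to follow-up blood pressure by name.

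**The concern.** The authors separated the value from the category in the NICU list, but for follow-up they listed only the category. Other follow-up outcomes do not have this gap: body composition by Pea Pod and Dexascan, Bayley scores and serum levels are all listed as measured quantities.

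Cutting a measured pressure at a threshold discards information, and this is a small trial. Aim 2 asks whether the intervention reduces findings suggestive of metabolic syndrome in the first 3 years, and Section 1 gives the purpose as preliminary data for a multicenter trial. A yes/no comparison in fewer than 100 children could easily miss a moderate shift in systolic pressure. With no threshold written down, even the yes/no result is not fixed in advance. If a continuous analysis is run later, it will be an unlisted one chosen after the fact.

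**Working it through.** **The plan's own figure.** There is none for this endpoint. Section 14 gives power only for weight and length velocity. The one figure used from it is the evaluable number: 150 × 2/3 = 100.

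**Inputs from the documents**
- 100 infants evaluable at 36 weeks (Section 14), allocated 1:1 (Section 4, Randomization).
- Clinic follow-up above 95% (Section 1). 100 × 0.95 = 95, or 47 per arm rounded down.

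**Inputs assumed, because the plan does not give them**
- Systolic pressure is normal, with the same SD in both arms and a uniform shift of *d* SD (0.3, 0.5 or 0.67).
- The proportion of controls counted as high, *p0*, is 10%, 20%, 30% or 40%.
- One visit, two-sided alpha 0.05, no allowance for clustering of multiples.

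**Continuous scale.** Two-sample t-test with 2n − 2 = 92 degrees of freedom and noncentrality d × √(n/2). For d = 0.5 this is 0.5 × √23.5 = 2.42, against a critical value of 1.99. Power is 67%.

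**Yes/no scale.** The cut is z = Φ⁻¹(1 − p0), and the treated proportion is p1 = 1 − Φ(z + d). For p0 = 20% and d = 0.5: z = 0.842, and p1 = 1 − Φ(1.342) = 9.0%. For p0 = 10%, p1 = 3.7%. Power is that of the uncorrected chi-square test, by exact enumeration of the two binomials.

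| Shift *d* | Continuous | p0 = 10% | p0 = 20% | p0 = 30% | p0 = 40% | Points lost |
|---|---|---|---|---|---|---|
| 0.3 SD | 30% | 14% | 17% | 18% | 20% | 10 to 16 |
| 0.5 SD | 67% | 25% | 35% | 40% | 45% | 22 to 42 |
| 0.67 SD | 90% | 35% | 52% | 61% | 68% | 22 to 55 |

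The last column is the difference of the rounded values.

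**Sensitivity**
- With 40 per arm at 0.5 SD, power is 60% continuous against 21% to 39% yes/no. Further attrition or clustering therefore lowers both figures but does not close the gap.
- Widening the assumptions to 0.3 to 0.8 SD and 5% to 50% of controls high, a normal approximation at 47 per arm gives a loss of about 9 to 73 points.

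**The visits side by side.** Section 1 places the blood-pressure endpoint at 6 months, 1, 2 and 3 years. The two-reading schedule covers 12 months, 18–26 months adjusted and 36 months. The 6-month endpoint has no listed reading behind it, so the calculation above is per visit and does not pool four visits.

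**The case against.** The strongest reply is that the plan does not bind itself to a yes/no analysis. Section 14 sends continuous variables generally to a t-test and generalized linear model, leaves secondary outcomes open, and the readings are listed as study measurements. This stands. A reader might infer that the plan restricts follow-up blood pressure to a dichotomy, but the text does not say so. It names only the dichotomy as an endpoint and leaves the rest unstated.

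Second, the size of the loss is not a document figure. This also stands. A single range such as 20 to 40 points is roughly the 0.5 SD row and is not a property of the plan. All cases assume a uniform normal shift. An effect confined to the upper tail was not computed and would favour the continuous scale less.

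Third, a reader might infer that the trial will leave no mean difference or SD for planning the next study. That does not follow, because both can be calculated from the raw readings whatever the endpoint is called. Nor would a null result here make Aim 2 uninformative, since it also has lipid, adipokine, body-composition and Bayley endpoints.

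Fourth, the secondary hypothesis is about reducing risk, which a proportion answers directly. That is a good reason to keep the percentage high, but not a reason to omit the value. The measurement protocol does cite a report on diagnosing high blood pressure in children. The citation is attached to how pressure is measured, and the plan does not say that it supplies the cut-off.

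**Conclusion.** The point holds as one of endpoint choice. At follow-up the only listed blood-pressure endpoint is a cut without a threshold, and the better-powered alternative needs only readings that are already scheduled at three visits. Under the stated assumptions (47 per arm, one visit, two-sided alpha 0.05, normal mean shift of 0.3 to 0.67 SD, 10% to 40% of controls high) the yes/no analysis gives up about 10 to 55 points of power. The direction is the same in every case computed; the size depends on assumptions that the plan does not supply.

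A reader might also take it that two readings exist at every visit at which the endpoint is named. The schedule does not support that for 6 months. This is one component of one secondary endpoint, and it does not touch the primary analysis.

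**What to change.** 1. In the secondary endpoint lists of Sections 1 and 3, add follow-up systolic pressure as a continuous endpoint: the mean of the two calm readings, or a z-score against a named reference.
2. In Section 14, state that it will be compared between arms at each visit where it is measured, using the generalized linear model already planned for continuous variables, and reported as a mean difference with 95% CI.
3. Keep high systolic pressure as a supporting result (percentage per arm and relative risk), with its cut-off and reference stated.
4. Reconcile the 6-month blood-pressure endpoint in Section 1 with the follow-up measurement schedule in Section 3, which lists no 6-month reading.

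The first three changes cost only wording, with no new visit, patient or measurement at the three scheduled visits. What the fourth costs depends on how the 6-month visit is resolved. The one downside is that a mean difference is slightly less direct to read clinically than a percentage high, which is still reported.
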